### **4. Specific Aims**

**Aim 1.** To conduct a Phase 1/2a, open-label, multi-center, multiple ascending dose study of intravenous adrabetadex to evaluate the safety and tolerability in treating cholestatic liver disease in infants with NPC1

**Aim 2.** To evaluate the efficacy of intravenous adrabetadex to reduce plasma levels of an NPC bile acid biomarker (glycine-conjugated trihydroxycholanic acid)

**Aim 3.** To evaluate the dose-response relationship for adrabetadex to attenuate liver dysfunction, as determined by reduction in serum transaminases and liver size and exploratory research outcome measures (e.g., NPC1 disease and inflammatory biomarkers)

## 5. Study Design and Methods

### 5.1 Study Overview

The trial will be a Phase 1/2a, open-label, dose-escalation, multi-center study of adrabetadex in subjects with NPC dosed twice a week with IV adrabetadex for six weeks for a total of 12 administrations, followed by a six month open-label extension phase in which the subjects are dosed monthly with IV adrabetadex for six months for a total of six administrations. The study will characterize the safety, tolerability, preliminary efficacy, and pharmacodynamics of IV adrabetadex. The primary outcome will be the efficacy of adrabetadex to reduce plasma levels of an NPC bile acid biomarker, a cholesterol-derived NPC1 disease-specific biomarker that serves as a pharmacodynamic (PD) measure of the effect of the drug to reduce the oxidizable cholesterol pool in liver tissue. The secondary outcome measure will be the examination of the dose-response relationship for attenuation of liver dysfunction, as determined by reduction in serum transaminases (ALT and AST) and liver size. This study will also evaluate the effect of intravenous adrabetadex on a series of disease-associated serum biomarkers.

### 5.2 Subjects

Approximately 12 subjects will be diagnosed as having either NPC1 or NPC2 based on criteria specified in Section 5.4.1. Information about this study will be disseminated through patient support organizations and posted on ClinicalTrials.gov. The research group may facilitate diagnostic testing. Both genders will be enrolled. No exclusion will be based upon race or ethnicity.

### 5.3 Study Size, Duration and Location

The study will enroll approximately 12 subjects up to a maximum of 15 subjects to account for potential study withdrawals, discontinuations or unconfirmed diagnosis of NPC. It is anticipated that this study will take four years to complete, with approximately four subjects to be enrolled per year.

Study-related assessments will be conducted at St. Louis Children's Hospital.

For each subject, the first phase of the protocol will be conducted over seven weeks; one-week inpatient followed by five weeks outpatient administrations with a post-dose safety evaluation performed one week after the final dose. The second phase of the protocol will be an open label extension conducted in an out-patient setting over six months with a post-dose safety evaluation performed one week after the final dose.

### 5.4 Eligibility Criteria

#### 5.4.1 Inclusion Criteria

1. Age 0 to 6 months of age at time of enrollment, both genders, and any race/ethnicity.
2. Diagnosis of NPC (either NPC1 or NPC2) based upon meeting any of the two following conditions:
  - A. Two variants classified as pathogenic or likely pathogenic in *NPC1/NPC2* on clinical laboratory testing , or
  - B. One variant classified as pathogenic or likely pathogenic on clinical laboratory testing and a positive NPC biochemical marker (oxysterol or bile acid biomarker or PPCS/Lyo509) test, if acid sphingomyelinase deficiency and cholesterol ester storage disease have been excluded either by clinical molecular testing of the *SMPD1* and *LIPA* genes or by clinical biochemical assay for acid sphingomyelinase and lysosomal acid lipase enzymes (or a combination of enzymatic and molecular testing).
3. Subjects with evidence of NPC-related liver disease as defined by direct bilirubin (DB) >2mg/dL or DB/total bilirubin ratio >0.2.

Variants will be interpreted using the American College of Medical Genetics guidelines for the interpretation of sequence variants and testing must be performed by a CLIA-certified laboratory.

4. Ability to travel to a research site.
5. Willing to participate in all aspects of trial design including serial blood collections.
6. Parent / guardian must provide written informed consent to participate in the study. Because of the age range intended for inclusion, assent will not possible.

#### **5.4.2 Exclusion Criteria**

1. Age > 6 months at time of enrollment in the trial.
2. A medical condition (such as clinically significant bleeding diathesis or evidence of immune suppression) that in the opinion of the investigator precludes placement of an intravenous catheter
3. An absolute neutrophil count (ANC) of less than 1,500 per microliter.
4. A platelet count less than 75,000 per microliter.
5. History of severe neonatal encephalopathy, per modified Sarnat including level of consciousness as stupor/coma, absent spontaneous activity, decerebrate posture, flaccid tone, absent suck, absent moro, diverted/nonreactive pupils, lack of heart rate variability, and apnea..
6. Subjects, who in the opinion of the investigators, are unable to comply with the protocol or have specific health concerns that would potentially increase the risk of participation. Examples of inability to comply include unwillingness to relocate or travel to a study site, suspected noncompliance with study procedures, behavior that jeopardizes the safety or security of the data or study staff, and other causes of inability to comply.
7. Concurrent participation in another investigational drug trial.
8. History of renal disease or evidence of acute kidney injury defined as serum creatinine greater than 1.5 mg/dL or an increase of at least 0.2-0.3 mg/dL per day.

#### **5.5 Prior and Concomitant Medications**

All concomitant medications will be recorded in the appropriate case report form (CRF).

#### **5.6 Dosing and Dose Adjustments**

Adrabetadex will be administered intravenously to specifically target liver disease. In the first phase of the study, dosing frequency will be twice a week with IV adrabetadex for six weeks for a total of 12 administrations. Subjects will be evaluated at each study visit for evidence of adverse effects.

Adrabetadex is provided as a 200 mg/mL solution and infused at this concentration and will be administered at a rate of 250 mg/kg/hr. A 5 kg infant receiving a 500 mg/kg dose, for example, will receive 12.5 ml of the 200 mg/ml solution.

Doses to be studied are 500 and 1000 mg/kg.

Six subjects will be studied at each dose level

Cohort 1	Subjects 1-6	500 mg/kg
Cohort 2	Subjects 7-12	1000 mg/kg

The DSMC will review data from the first phase of the study for all six subjects in Cohort 1 prior to initiation of Cohort 2.

Subjects who do not tolerate (section 7.9) the initial 500 mg/kg dose may have the dose decreased to 250 mg/kg/dose and remain at this dose for the remainder of the study.

Subjects who do not tolerate the 250 mg/kg dose will be withdrawn from the study.

Subjects who do not tolerate the first two doses of 1000 mg/kg dose may have the dose decreased to 500 mg/kg and remain at this dose level for the remainder of the study.

Subjects may be withdrawn for any Grade 3 AE (per NCI's CTCAE) possibly, probably or definitely related to study drug; any Grade 4 toxicity; any subject with pulmonary complications or evidence of renal injury; or determination that the limit of safety and/or tolerability has been reached. In the context of adrabetadex administration, limit of tolerability is defined as a sustained increased respiratory rate over 30 minutes or decreased SaO2 (<90%) resulting in need for, or increase in sustained need for supplemental oxygen, or evidence of renal injury as defined as a serum creatinine (SCr) rise > 0.5 mg/dl.

Subjects who demonstrate significant reduction either in the glycine-conjugated trihydroxycholanic acid biomarker or serum bilirubin (direct bilirubin or direct bilirubin:total bilirubin ratio) will be allowed to crossover into the second phase of the study, an open-label phase of six months duration. In this phase of the study, dosing frequency will be monthly with IV adrabetadex for six months for a total of six administrations. Subjects will be evaluated at each study visit for evidence of adverse effects.

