## **7.7 Subject Withdrawal**

Guardians/parents will be informed that they have the right to withdraw from the study at any time for any reason without prejudice to their medical care. Subjects may be withdrawn from the study for any of the following reasons:

- Parent/guardian request
- Parent/guardian is unwilling or unable to comply with the protocol
- Medical reason, at the discretion of the Investigator or Medical Monitor
- Occurrence of the following:
  - a. any Grade 3 AE (per NCI's CTCAE) possibly or definitely related to study drug
  - b. any Grade 4 toxicity
  - c. any subject with pulmonary complications or evidence of renal injury
  - d. determination that the limit of safety and/or tolerability has been reached. In the context of adrabetadex administration, limit of tolerability is defined as a new oxygen requirement or evidence of renal injury.
  - e. evidence of development or worsening of liver synthetic function (monitored by serum albumin and PT) or evidence of development or worsening of hepatic encephalopathy (monitored by serum ammonia levels).

Although study treatment will cease, subjects will be encouraged to remain on study in order to collect all of the data prescribed in the protocol. The reasons for subject withdrawal will be recorded in the subject's CRF.

For a withdrawal due to a safety issue, subjects will be followed until the safety issue is resolved or returns to baseline level. Additionally, any appropriate referrals will be made as needed.

Any usable data from withdrawn subjects will be included in safety and efficacy evaluations. Withdrawn subjects may be replaced.

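### Sections 5.6, 7.7, 7.8, Table 1 and 9.11 give different actions for the same event in an individual infant and define the tolerability limit differently

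*Combined protocol and SAP*

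**What the plan says.** Rules for an individual infant stand in five places.

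- **5.6** allows withdrawal on a list of grounds ("Subjects may be withdrawn for any Grade 3 AE" with at least a possible link to study drug is one). It sets a limit: "limit of tolerability is defined as a sustained increased respiratory rate over 30 minutes or decreased" SaO2 (below 90%) that leads to a new or greater need for oxygen, or "evidence of renal injury as defined as a serum creatinine (SCr) rise" above 0.5 mg/dL. It also provides a step-down: "Subjects who do not tolerate (section 7.9) the initial 500 mg/kg dose may have the dose decreased to 250 mg/kg/dose". For the higher cohort: "Subjects who do not tolerate the first two doses of 1000 mg/kg dose may have the dose decreased to 500 mg/kg".
- **7.7** opens its list with "Subjects may be withdrawn from the study for any of the following reasons". The list includes "any Grade 4 toxicity" and a second definition: "limit of tolerability is defined as a new oxygen requirement or evidence of renal injury".
- **7.8, text** refers safety and tolerability to Table 1, except respiratory and audiological events. It then requires withdrawal or dose reduction for named systemic signs (allergic rash among them), respiratory signs or neurological signs that appear during the infusion or in the 2 hours after it. It requires the same choice for an infiltrate on chest X-ray that is likely due to the drug.
- **Table 1** excludes respiratory and audiological events in its title. Row A repeats the dose after any number of Grade 1 drug-related AEs. Row D withdraws the infant for a drug-related Grade 3 or 4 AE, for a drug-related pulmonary complication, or when the limit of safety or tolerability is reached.
- **9.11** repeats the step-downs in 5.6, tied to the first dose at 500 mg/kg and the first two at 1000 mg/kg, and gives tolerability decisions to the DSMC together with the investigators and the local monitor.

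**The concern.** A clinician at the bedside needs one answer to whether this infant receives the next infusion, and at what dose. If the answer depends on the section opened, two infants with the same event can be treated differently, and one may be re-exposed when another rule would have reduced or stopped the drug. Enrolment is at 0 to 6 months of age, and section 8.2 says that the risks of the intravenous drug are not known. The DSMC also reviews all six infants of Cohort 1 before 1000 mg/kg opens, so it should be able to rely on tolerability having been judged by one standard.

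**Working it through.** No formula applies. The check sets the rules side by side for the same event.

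| Event | One rule | Another rule | Same action? |
|---|---|---|---|
| Infiltrate likely due to drug | 7.8 text: withdraw or reduce | Row D, pulmonary complication: withdraw | No |
| Grade 1 drug-related rash during infusion | 7.8 text: withdraw or reduce | Row A: repeat the dose | No |
| Tolerability limit reached at dose 1 of 500 mg/kg | 5.6 and 9.11: may reduce to 250 mg/kg | Row D: withdraw | No |

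**Infiltrate.** The table's title and the opening of 7.8 both take respiratory events out of Table 1, yet row D lists a pulmonary complication. The table departs from its own scope, and its action leaves no room for the reduction that the text allows.

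**Rash.** A rash is not respiratory, so the exclusion does not settle it. The 7.8 text makes a change mandatory; row A prescribes none.

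**Limit at dose 1.** The step-down in 5.6 applies to an infant who does not tolerate the dose, and for that term it cites 7.9. Section 7.9 covers termination and interruption of the whole study and defines no individual intolerance. The natural substitute is the limit of tolerability defined later in 5.6, but reaching that limit is a withdrawal event in row D.

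**The limit itself.**

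| Part | 5.6 | 7.7 | 7.8 text |
|---|---|---|---|
| Respiratory | Raised rate or SaO2 <90%, with new or greater oxygen need | New oxygen requirement | Raised rate or SaO2 <90%, no oxygen condition |
| Time window | None | None | During infusion or within 2 hours after |
| Renal | SCr rise >0.5 mg/dL | Renal injury, no threshold | Not covered |

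Three cases show the effect:

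1. SaO2 of 88% during the infusion with no oxygen given: 7.8 requires withdrawal or reduction, but neither the 5.6 nor the 7.7 limit is met.
2. A new oxygen requirement more than 2 hours after the infusion: the 7.7 limit is met, but the 7.8 infusion-time rule is not triggered.
3. A creatinine rise of 0.5 mg/dL or less: the 5.6 limit is not met, but 7.7 could be. The entry criteria (5.4.2, item 8) already count a rise of 0.2-0.3 mg/dL per day as acute kidney injury.

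**The case against.** Much of the text can be reconciled. The list in 7.7 includes parental request, so *may be withdrawn* reads as a list of grounds, with Table 1 setting the action. For Grade 4, permission in any case and obligation when drug-related differ only in scope. On timing, 5.6 and 9.11 permit early step-down without forbidding a later one, and *initial* in 5.6 may mean the starting dose level. Section 9.9 only carries the dose-12 level forward. All of this stands. A reader might infer that the plan contradicts itself on Grade 3 or Grade 4 events, or bars reduction after the early doses. The documents do not support that; these are ambiguities.

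It can also be said that the specific 7.8 rule naturally overrides the general row A. That is the ordinary reading, but the plan states no precedence, and this reading does not settle the pulmonary item or the limit.

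Oversight is real: the DSMC's role in 9.11, weekly investigator review during admission (11.4), DSMC review after the first two completers and each one after (11.5), and the study-level rules in 7.9 and 11.4.2. It reduces the risk. It does not supply a single rule to apply, and 11.4.1 describes the Principal Investigator as reviewing individual tolerability with input from others, including the DSMC.

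Finally, the asterisk in Table 1's column heading has no footnote in the text available, and rows A and B contain broken phrases. A lost note could soften row A or D. It would be unlikely to align the definitions in 5.6 and 7.7, or to correct the pointer.

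**Conclusion.** The concern holds in limited form. Three events carry different written actions, the tolerability limit has two unequal definitions with a third set of respiratory criteria in 7.8, and one cross-reference leads to a study-level rule. It should be fixed; it does not undermine the design.

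The conclusion rests on three assumptions: that Table 1 as read is complete on rows A and D; that not tolerating a dose in 5.6 means reaching the limit of tolerability, since nothing else defines it; and that the oxygen condition in 5.6 attaches to both respiratory signs. The SaO2 case above does not need the last one.

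A reader might go further and infer a measurable distortion of the safety results. The documents give no event rates from which to size one. A single event's CTCAE grade does not change with the rule applied, and 7.7 keeps usable data from withdrawn infants in the evaluations. The case for change is consistent protection of the infant.

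**What to change.** 1. **Precedence.** State in 5.6, 7.7 and 7.8 that Table 1 governs drug-related AEs, that the 7.8 infusion-time rule overrides rows A and B, and that where two rules apply the stricter action is taken.
2. **Respiratory events.** Keep withdrawal for drug-related Grade 3-4 events, respiratory ones included. For lower-grade respiratory events and infiltrates use the 7.8 text (withdraw or reduce). Amend row D's pulmonary item and the table title to match.
3. **One limit in 5.6 and 7.7.** Keep the present triggers: a new or increased oxygen requirement at any time, the 7.8 respiratory signs during infusion or within 2 hours, or an SCr rise above 0.5 mg/dL. Referring to 7.8 alone would lose a later oxygen requirement that meets 7.7 today. The DSMC should confirm the renal threshold, because 7.7 now has none. If the sponsor intends a raised rate without oxygen need to count at any time, say so.
4. **Step-down.** State whether reaching the limit at the early doses permits the reduction in 5.6 and 9.11 or requires withdrawal under row D, and whether reduction is allowed later. Without this, the stricter-action rule would turn any 7.8 respiratory sign that counts as the limit into a withdrawal.
5. **Pointer.** Replace the reference to 7.9 in 5.6 with 7.8 and Table 1.

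The cost is an amendment and slightly less investigator discretion. Items 3 and 4 need a clinical decision from the sponsor and the DSMC. No visit or blood draw is added.

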## **5.7. Biological Specimens**

Blood (serum and plasma) and urine will be collected as part of this protocol. Research samples will be stored locally or in the NICHD biorepository. Coded samples may be sent to collaborating laboratories, the NIH, and Mandos, LLC. Biomaterial collected as part of this study may be used for future research related to Niemann-Pick disease or other projects specifically approved by an Institutional Review Board. Priority will go to studies related to Niemann-Pick disease.

## **5.8 Non-study Drugs**

This protocol will not provide non-study drugs.

## **5.9 Study Drug**

Mandos, LLC will provide the study drug and support regulatory aspects of this study. Adrabetadex will not be provided under this protocol after completion of this study.

## **5.12 Withdrawal of Subjects from the Study**

Subjects that are withdrawn from the study either by their choice or investigator action will be provided with written notification that their child was withdrawn from the study and provided with written recommendations regarding clinical follow-up.

# **6. Assessments, Procedures, and Testing**

## **6.1 Medical History and Physical/Neurological Examinations**

A medical and medication history will be obtained and a physical exam will be conducted after admission to the study center. This will ensure that the subject's medical health is adequate to participate in this study.

Subjects will be evaluated with an interim history and physical examination at least daily while admitted to the study center.

Anthropomorphic measures including weight and height will be obtained weekly in phase 1 and monthly in phase 2.

Physical and neurological examinations will be standardized.

## **6.2 Pulmonary Function Assessment**

A baseline CXR and oxygen saturation will be obtained to assess placement of a peripherally inserted central catheter (PICC) and prior to the first administration of the study drug. CXR will only be repeated if clinically indicated.

## **6.3. Liver function assessment**

In phase 1, plasma AST and ALT will be obtained at baseline, 2, 4 and 6 weeks. In phase 2, plasma AST and ALT will be obtained at baseline, 2, 4 and 6 months.

## **6.4 Abdominal Ultrasound**

In phase 1, an abdominal ultrasound exam will be conducted at baseline and 6 weeks to determine liver size and spleen volumes. Liver size is determined by the liver's midclavicular longitudinal diameter (34). Organ volumes are the product of three long axes (longitudinal, transverse and anterior-posterior) (35). At the time of this abdominal ultrasound in phase 1, liver elastography will also be obtained. In Phase 2, an abdominal ultrasound with liver elastography will be repeated at the end of the six-month protocol.

## **6.5 Audiological Evaluation.**

An audiological evaluation will be obtained at baseline and at conclusion of phase 1 of the study. Audiology assessment will be performed using otoacoustic emissions (OAE). This test does not require sedation.

## **6.6 Clinical Laboratory Tests**

Clinical laboratory testing will be conducted by St. Louis Children's Hospital Clinical Laboratories.

### **6.6.1 Hematology/Chemistry**

Blood samples for the clinical laboratory tests will be collected by a qualified person using either the central line, by indwelling catheter, or by venipuncture.

Testing will include the following (phase 1: 2.5 mls/time point; 10 mls total over six weeks, phase 2: 2.5 mls/time point; 10 mls total over six months):

Hematology: complete blood count (CBC) with differential and platelet count, and prothrombin time (PT).

Clinical chemistry: electrolytes, glucose, blood urea nitrogen (BUN), creatinine, AST, ALT, GGT, alkaline phosphatase, bilirubin (direct and total), albumin, calcium, magnesium, phosphorus, and CK.

In phase 1, testing will occur at baseline, 2, 4 and 6 weeks. In phase 2, testing will occur at baseline, 2, 4, and 6 months. For study subjects, the amount drawn will not exceed the lesser of 50 ml or 3 ml per kg in an 8 week period and collection may not occur more frequently than 2 times per week.

Lab results do not need to be resulted and reported prior to dosing.

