## **6.7 Research Laboratory Testing**

Plasma and serum will be collected for biomarker analysis. Sample collection, processing and storage will be standardized. Coded samples will be sent to NICHD Biorepository for long-term storage. Testing may be performed in clinical or research laboratories. Research testing will include, but is not limited to the following:

Markers of cholesterol homeostasis (phase 1: Baseline, 2, 4 and 6 weeks; 0.5 ml/time point; 2 mls total over 6 weeks; phase 2: Baseline, 2, 4 and 6 months; 0.5 ml/time point; 2 mls total over 6 months)

1. Trihydroxycholanic acid glycine conjugate (bile acid biomarker)
2. Cholestan-3 $\beta$ ,5 $\alpha$ ,6 $\beta$ -triol
3. PPCS/Lipid-509

Plasma lipidomics (phase 1: Baseline and 6 weeks; 0.5 ml/time point; 1 ml total over 6 weeks; phase 2: 6 months; 0.5 ml/time point; 0.5 ml total over 6 months)

1. Sphingolipids: sphingoid bases, ceramides, glucosylceramides, lactosylceramides, gangliosides
2. Lysosphingolipids: lyso-sphingomyelin

Additional biomarkers for NPC (phase 1: Baseline, 2, 4, and 6 weeks; 1.75ml/time point; 7mls over 6 weeks; phase 2: Baseline, 2, 4, and 6 months; 1.75 ml/time point; 7 mls total over 6 months)

- Serum 24(S)-hydroxycholesterol
- Serum 27-hydroxycholesterol
- Serum neurofilament light chain

Lab results do not need to be resulted and reported prior to dosing.

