### **8.3 Phlebotomy**

Phlebotomy is a risk/discomfort of this study. An anesthetic cream such as EMLA is an option to reduce discomfort. Infection and bruising are possible at the site of the blood draw. At each time point the maximum blood draw is 6 mL. In Phase 1, the maximum blood draw over 6 weeks is 24mL. In Phase 2, the maximum blood draw over 6 months will be 24mL. Nursing staff will monitor blood-drawing volumes. If blood limits are an issue, testing will be prioritized by the investigators. Safety laboratory tests will take priority over investigational testing. Not obtaining a test due to blood limit prioritization will not be considered a protocol deviation.

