## 11.8 Protocol Deviations

The following anticipated minor deviations in the conduct of the protocol will not be reported to the site IRBs unless they occur at a rate greater than that which is anticipated to occur (frequency will be assessed on a 12 month basis).

	Expected Frequency
Inability to obtain a blood or urine sample	15%
Technical issues preventing analysis of a blood Sample (e.g. hemolysis)	15%
Procedure or sample not obtained at specified time	15%
Drug administration occurring outside of defined time range	10%

Not obtaining a test due to blood limit prioritization will not be considered a protocol deviation.

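### The Phase 1 blood schedule and the 24 mL maximum do not fit the 3 mL/kg cap in lighter infants if the cap covers all study blood, and the primary biomarker sample is not ranked above exploratory samples

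*Combined protocol and SAP*

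**What the plan says.** Section 6.6.1 sets a cap: "For study subjects, the amount drawn will not exceed the lesser of 50 ml or 3 ml per kg in an 8 week period". The same section schedules 2.5 mL of hematology and chemistry at baseline and at weeks 2, 4 and 6.

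Section 6.7 adds three research groups in Phase 1:
- cholesterol-homeostasis markers, which include the primary bile acid biomarker, at all four visits ("0.5 ml/time point; 2 mls total over 6 weeks");
- lipidomics at baseline and week 6 ("0.5 ml/time point; 1 ml total over 6 weeks");
- 24-OHC, 27-OHC and neurofilament light chain (NfL), 1.75 mL at all four visits.

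Section 6.8 lists a further optional 0.5 mL for inflammation markers at baseline and weeks 4 and 6.

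Section 8.3 then states: "At each time point the maximum blood draw is 6 mL", and "In Phase 1, the maximum blood draw over 6 weeks is 24mL". Neither sentence mentions weight. It continues: "If blood limits are an issue, testing will be prioritized by the investigators", with one rule of order: "Safety laboratory tests will take priority over investigational testing". Sections 8.3 and 11.8 both add: "Not obtaining a test due to blood limit prioritization will not be considered a protocol deviation".

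Section 10 makes the plasma bile acid biomarker the primary outcome, and section 3 places the evaluation after the 12 doses. Section 5.4.1 enrols infants aged 0 to 6 months. The only body weight in the protocol is 5 kg, used to illustrate dosing in sections 5.6, 9.4 and 9.9.

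**The concern.** Each subtotal in the protocol is right. The difficulty lies between passages. One sets a limit that scales with weight; the others give a fixed schedule and a fixed maximum for infants young enough that the weight-based limit may govern. The 50 mL limb of the cap plays no part below 16.67 kg (50 / 3).

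Where the cap binds, something must be left out. The plan protects safety tests and leaves the rest to the investigators' choice. It does not place the primary sample ahead of exploratory ones or reserve volume for week 6, and an omitted primary sample would not be recorded as a deviation. At stake are the week-6 change in the primary outcome for some lighter infants and, to a lesser extent, the biomarker route into Phase 2 in section 9.9.

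**Working it through.** **Inputs.** Volumes come from sections 6.6.1, 6.7 and 6.8, the maximum from section 8.3, and the 3 mL/kg cap from section 6.6.1. The four draws are scheduled over six weeks, so they fall within one eight-week window.

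**The plan's own figures.** 4 × 6 mL = 24 mL, as section 8.3 states. The subtotals also reproduce: 4 × 2.5 = 10; 4 × 0.5 = 2; 2 × 0.5 = 1; 4 × 1.75 = 7; 3 × 0.5 = 1.5 mL.

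**Scheduled volume by visit (mL).**

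| | Baseline | Week 2 | Week 4 | Week 6 | Total |
|---|---|---|---|---|---|
| Without section 6.8 | 5.25 | 4.75 | 4.75 | 5.25 | 20.0 |
| With section 6.8 | 5.75 | 4.75 | 5.25 | 5.75 | 21.5 |

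Every visit is within the stated 6 mL.

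**Lowest weight at which each volume fits** (volume / 3 mL/kg), if the cap covers all study blood:
- schedule: 20.0 / 3 = 6.67 kg; with section 6.8, 21.5 / 3 = 7.17 kg
- stated maximum: 24 / 3 = 8.0 kg

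If the cap covers clinical laboratory tests only: 10 / 3 = 3.33 kg.

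**Volume that must be omitted or reduced** (total − 3 × weight), all-blood reading:

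| Weight | Cap (mL) | Without 6.8 | With 6.8 |
|---|---|---|---|
| 4 kg | 12 | 8.0 | 9.5 |
| 5 kg | 15 | 5.0 | 6.5 |
| 6 kg | 18 | 2.0 | 3.5 |
| 7 kg | 21 | 0 | 0.5 |

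**Can the primary samples be kept?** Safety tests plus all four primary samples need 10 + 2 = 12 mL, which fits from 12 / 3 = 4.0 kg. Safety tests plus only the baseline and week-6 primary samples need 10 + 1 = 11 mL, which fits from 3.67 kg.

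**How a week-6 value could be lost at 5 kg.** Suppose baseline and week 2 are drawn in full, week 4 is cut to safety tests, and week 6 to safety tests plus the primary sample:
- without section 6.8: 5.25 + 4.75 + 2.5 + 3.0 = 15.5 mL
- with section 6.8: 5.75 + 4.75 + 2.5 + 3.0 = 16.0 mL

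Against 15 mL, the shortfall is 0.5 or 1.0 mL.

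**The case against.** The strongest reply is that a fixed maximum and a weight-based cap are simply two ceilings, and obeying the lower breaches neither. Section 8.3 foresees the problem: nursing staff track volumes, safety tests come first, and the investigators decide the rest. This stands to the extent that the cap can always be obeyed by omitting tests, except that below 3.33 kg the safety tests alone exceed it. It does not make the itemised schedule feasible at low weight, or the 24 mL figure correct below 8.0 kg.

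Second, the cap appears under clinical laboratory tests and may cover only those. That reading cannot be excluded. The wider one is more natural because the wording refers to the amount drawn from study subjects, and ranking safety over investigational tests has a purpose only if both share one limit.

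Third, nothing suggests that investigators would sacrifice the primary endpoint. The loss shown at 5 kg requires full early draws with no planning. Skipping one 1.75 mL draw avoids it. So does a gain of 0.17 kg (0.5 / 3) or 0.33 kg (1.0 / 3), if current weight sets the cap. This stands, and it makes the loss avoidable rather than expected.

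A reader might infer three stronger conclusions that the documents do not support:
- *The trial loses power.* Section 10 states about 80% power for a 33% reduction in 5 subjects, and each cohort has 6. A fall below 5 requires two lost week-6 values in one cohort. Its size also depends on an assumed SD of change and a two-sided paired t test at 0.05. The SD back-solved from the stated 80%, 19.6 percentage points, gives about 62% with four subjects. The SD of the three reductions quoted in section 10 (46, 62 and 75%), 14.5 points, gives about 84%.
- *Phase 2 entry fails.* Section 9.9 also admits infants on bilirubin, which is in the protected safety panel. Only an infant who would qualify on the biomarker alone is exposed.
- *Most infants are affected.* No weight distribution is given, so the share cannot be calculated.

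**Conclusion.** The inconsistency holds, conditional on what the cap covers. On the all-blood reading, the protocol schedules 5.0 to 6.5 mL more than the cap allows at its own example weight, and its stated maximum is 9 mL above the cap there (24 − 15). On the narrow reading, only infants below 3.33 kg are affected. The absence of any ranking for the primary sample is plain on either reading, though it matters mainly on the first.

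The thresholds use the stated volumes; smaller samples would lower them. The protocol also does not say whether baseline or current weight sets the cap, although section 6.1 has weight measured weekly in Phase 1. No specific power loss is claimed.

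This is a minor to should-fix point, held with moderate confidence because the cap can be read in two ways.

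**What to change.** (a) Reconcile the 24 mL maximum in section 8.3 and the itemised schedule in sections 6.6.1, 6.7 and 6.8 with the 3 mL/kg cap. State whether the cap covers all study blood and which weight sets it. The passages also need reconciling for infants below 3.33 kg. No volume limit is proposed here.

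(b) Add to section 8.3:

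> When blood volume is limited, after safety laboratory tests the primary bile acid biomarker sample has priority over all exploratory samples, and volume for the baseline and week-6 primary samples is reserved.

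The cost is a few sentences, handled as an amendment under section 13.5, and a short volume-planning step per subject. Lighter infants will yield fewer exploratory results: at 5 kg, keeping all four primary samples leaves 15 − 12 = 3.0 mL for exploratory samples scheduled at 8.0 mL (9.5 mL with section 6.8). On the all-blood reading the cap already forces that shortfall; the change settles which samples bear it.
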